10.3.1.2. Secondary Efficacy Analyses

10.3.1.2.1. Plasma Glucose Values

Descriptive statistics will be used to summarize the baseline, various postdose time points, and absolute change from baseline in PG values by treatment group. Additional analysis will be performed if deemed necessary. The details will be provided in the SAP.

If a patient receives additional intervention to raise PG concentrations, measurements taken after the time of intervention will be excluded from the analysis.

10.3.1.2.2. Symptoms of Hypoglycemia

Descriptive statistics will be used to summarize the baseline, various postdose time points, and absolute change from baseline in total score and each subscale score of Edinburgh Hypoglycemia Scale by treatment group. Additional analysis will be performed if deemed necessary. The details will be provided in the SAP.

10.3.2. Safety Analyses

10.3.2.1. Clinical Evaluation of Safety

All investigational products and protocol procedure AEs will be listed, and if the frequency of events allows, safety data will be summarized using descriptive methodology.

The incidence of symptoms for each treatment will be presented by severity and by association with investigational product as perceived by the investigator. Symptoms reported to occur prior to enrollment will be distinguished from those reported as new or increased in severity during the study.

The number of investigational product-related SAEs will be reported.

Nasal/respiratory and anosmia AEs will be identified using preferred terms and summarized by treatment group, the details will be provided in the SAP.

This section is applicable to spontaneously reported AE. Events solicited through Nasal and Non-nasal Score Questionnaire will be analyzed separately and the details are provided in Section [10.3.2.2](#).

10.3.2.2. Nasal and Non-nasal Score Questionnaire

The scoring for each response to Nasal and Non-nasal Score Questionnaire will follow the scale displayed on the questionnaire ('None'=0, 'Mild'=1, 'Moderate'=2, 'Severe'=3). The total score of the questionnaire will be calculated as the sum of the scores for each question. Descriptive statistics will be used to summarize the baseline, various postdose time points, and absolute change from baseline in total score of Nasal and Non-nasal Score Questionnaire by treatment group. See [Appendix 6](#) for a copy of the questionnaire. Additional analysis will be performed if deemed necessary. The details will be provided in the SAP.

10.3.2.3. Statistical Evaluation of Safety

Safety parameters will be assessed including safety laboratory parameters, vital signs, and ECG parameters. The parameters will be listed and summarized using standard descriptive statistics. Additional analysis will be performed if deemed necessary. The details will be provided in the SAP.

10.3.3. Pharmacokinetic Analyses

10.3.3.1. Pharmacokinetic Parameter Estimation

Pharmacokinetic parameter estimates for glucagon and DPC will be calculated using standard noncompartmental methods of analysis (NCA).

The primary parameters for PK analysis will be maximum drug concentration (C_{max}), area under the concentration versus time curve (AUC), time to maximal concentration (T_{max}) of glucagon and DPC. Other noncompartmental parameters, such as half-life, apparent clearance, and apparent volume of distribution may be reported.

Parameters will be individually calculated for each subject based on actual time of collection.

10.3.3.2. Pharmacokinetic Statistical Inference

Log-transformed PK parameters (such as C_{max} and AUC parameters) will be evaluated in a linear mixed-effects model with fixed effects for treatment, period, and sequence, and a random effect for patient. The treatment differences will be back-transformed to present the ratios of geometric means and the corresponding 90% CI.

The T_{max} will be analyzed using the Wilcoxon signed rank test. Estimates of the median difference based on the observed medians, 90% CIs, and p-values from the Wilcoxon test will be calculated.

Exploratory analyses may be performed for other PK parameters as deemed appropriate.

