Nasal inspection		X		Nasal inspection should be conducted before the procedure to induce hypoglycemia and at 90 minutes postglucagon administration
Injection-site inspection (for IM glucagon only)		X		The injection site will be inspected before the procedure to induce hypoglycemia to confirm injection site is normal and at 90 minutes postglucagon administration
Nasal and Non-nasal Score Questionnaire		X		See Appendix 6, Nasal and Non-nasal Score Questionnaire. Questionnaire to be completed approximately 30 minutes prior to hypoglycemia induction and 15, 30, 60, and 90 minutes postglucagon administration

Edinburgh Hypoglycemia Scale		X		See Appendix 7 , Edinburgh Hypoglycemia Scale. This questionnaire should be completed when $PG \leq 75$ mg/dL and again at $PG \leq 60$ mg/dL after the start of the insulin infusion and at 15, 30, 45, and 60 minutes postglucagon administration
Insulin infusion to induce hypoglycemia		X		Refer to Sections 9.2 and 7.7 for details regarding this procedure, including steps to take before the procedure begins and steps to take if there is an insufficient response to glucagon administration. Procedures taking place on Period 2 will occur at approximately the same time as those for Period 1.
Study drug administration		X		Once PG reaches below 60 mg/dL, the insulin infusion is stopped and approximately 5 minutes later study drug is administered
Sample collection for measurement of glucagon		X	X	Samples will be collected pre-dose (i.e., immediately prior to glucagon administration) and at 5, 10, 15, 20, 25, 30, 40, 50, 60, 90, 120, and 240 minutes post-glucagon administration at Periods 1 and 2 and once at follow-up. All samples will be processed at a central laboratory.
Sample collection for measurement of DPC		X		Samples will be collected from NG-treated patients pre-dose (i.e., immediately prior to glucagon administration) and at 10, 20, 30, 40, 60, 120, and 240 minutes post-glucagon administration. Three additional samples may be collected. Samples to be processed at a central laboratory.

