5.1. Overall Design

This is a Phase 1, multicenter, randomized, open-label, 2-treatment, 2-period, crossover study. [Figure IGBI.1](#) illustrates the study design. In each period, patients with T1DM will undergo a procedure to induce hypoglycemia using insulin infusion. The insulin infusion will be used to decrease PG and will be stopped once PG <60 mg/dL and it is expected that PG will continue to decrease for an additional 15 to 20 mg/dL to its lowest concentration. Approximately 5 minutes after the insulin infusion is stopped, patients will be administered either 3-mg NG (LY900018) or 1-mg IMG (GlucaGen) in the deltoid muscle of the nondominant arm by CRU staff members. Serial blood sampling will be performed for glucagon and PG concentration assessments immediately before and up to 6 hours following administration of glucagon. Following each test period, patients will remain in the CRU for at least 6 hours following the procedure. All patients will receive a carbohydrate-rich meal prior to discharge. Patients may stay longer as needed, at the discretion of the investigator.

After a wash-out period of at least 1 day (24 hours) and no more than 7 days, patients will return to the clinic and the procedure repeated with each patient crossed over to the alternate glucagon treatment.

A CRU visit for follow-up or early discontinuation should occur approximately 28±2 days after the last dose of study drug.

Abbreviations: CRU = clinical research unit; IM = intra-muscular; T1DM = type 1 diabetes mellitus.

Figure IGBI.1. Illustration of study design for Protocol I8R-MC-IGBI.

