10.1. Sample Size Determination

Assuming a 5% dropout rate, the study will enroll approximately 70 patients to have 66 patients completing both treatment visits with evaluable primary outcome.

A total of 66 patients are required in the study in order to achieve the primary objective with at least 90% power under the following assumptions:

- A treatment success rate of 98% for both treatments
- A noninferiority margin of 10%
- One-sided alpha level of 0.025
- A within-patient correlation of zero between 2 treatment visits

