10.3.4.2. Pharmacodynamic Statistical Inference

The PD parameters (such as BG_{max} and AUEC parameters) will be log-transformed prior to analysis and a linear mixed-effects model fitted to the data, with treatment, period, and sequence as fixed effects and patient as a random effect. For each parameter, the treatment difference will be back-transformed to present the ratios of geometric means and the corresponding 90% CI.

The values of T_{\max} will be analyzed nonparametrically using the Wilcoxon signed-rank test. Median differences and approximate 90% CIs for the difference will be calculated for the comparisons of treatments.

Exploratory analyses may be performed for other PD parameters as deemed appropriate.

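### Section 10.3.3.2 pairs a glucagon Tmax estimate based on observed medians with, on the plain reading, a signed-rank 90% CI, so the estimate can fall outside its own interval

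*Protocol*

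**What the plan says.** The trial is a crossover with two treatments and two periods (section 5.1: "This is a Phase 1, multicenter, randomized, open-label, 2-treatment, 2-period, crossover study"), so each completing patient contributes a pair of Tmax values.

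For the PK parameter, section 10.3.3.2 says "The T_{max} will be analyzed using the Wilcoxon signed rank test". The next sentence fixes what is reported: "Estimates of the median difference based on the observed medians, 90% CIs, and p-values from the Wilcoxon test will be calculated". Section 10.3.3.1 adds "Parameters will be individually calculated for each subject based on actual time of collection". The Schedule of Activities (section 2) places post-dose glucagon samples "at 5, 10, 15, 20, 25, 30, 40, 50, 60, 90, 120, and 240 minutes post-glucagon administration".

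For the PD parameter, section 10.3.4.2 also uses the signed-rank test but words the output differently: "Median differences and approximate 90% CIs for the difference will be calculated for the comparisons of treatments". It does not mention observed medians.

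Tmax is listed under the secondary PK and PD objectives in section 4, and section 10.3.3.1 counts it among the main PK parameters. DPC is sampled only after nasal dosing, so the treatment comparison in 10.3.3.2 concerns glucagon Tmax.

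**The concern.** A confidence interval obtained by inverting the signed-rank test covers one particular quantity, the pseudo-median of the within-patient differences. The estimate that belongs with it is the Hodges-Lehmann estimate, the median of all pairwise averages (Walsh averages) of those differences. Section 10.3.3.2 instead bases the estimate on the observed medians. That phrase has two possible meanings, and neither is the pseudo-median:

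- the difference of the two treatment medians, which does not use the pairing;
- the median of the paired differences, which does use it.

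The quantities agree when the differences are symmetric and finely measured. Tmax is usually skewed and is read from a discrete set of draws, so they can separate. The study report could then show a treatment effect that its own interval excludes, or an estimate of zero beside an interval lying wholly above zero. At stake is the credibility of one secondary estimate, not a trial decision.

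**Working it through.** The protocol states no figure that depends on this rule, so there is none to reproduce. Two checks follow: a constructed example that needs no distribution, and a simulation.

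**Inputs.** 66 pairs, the number of completers that section 10.1 requires ("A total of 66 patients are required in the study in order to achieve the primary objective with at least 90% power"), assuming all have evaluable Tmax in both periods. Glucagon sampling times are those in section 2. The interval is a 90% signed-rank CI from ordered Walsh averages with a normal-approximation cut-off.

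**1. Constructed example.** Let 36 patients have Tmax 15 min on both treatments and 30 patients have 30 min on nasal and 15 min on intramuscular glucagon.

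- Treatment medians: 15 and 15, so their difference is 0.
- Paired differences: 36 zeros and 30 values of 15, so their median is also 0.
- Number of Walsh averages: 66 × 67 / 2 = 2,211.
  - equal to 0: 36 × 37 / 2 = 666
  - equal to 7.5: 36 × 30 = 1,080
  - equal to 15: 30 × 31 / 2 = 465
  - check: 666 + 1,080 + 465 = 2,211
- The middle value is the 1,106th. Ranks 667 to 1,746 are all 7.5, so Hodges-Lehmann = 7.5.
- Signed-rank mean: 66 × 67 / 4 = 1,105.5. Standard deviation: √(66 × 67 × 133 / 24) = √24,505.25 ≈ 156.5.
- 90% limits at ranks 1,105.5 ± 1.645 × 156.5, about the 848th and 1,363rd. Both are 7.5.

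The estimate is 0 under either reading and the interval is 7.5 to 7.5. If the zero differences are dropped, as some implementations do, the 30 that remain all equal 15. The interval is then 15 to 15, which also excludes 0.

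**2. Simulation.** 1,500 trials of 66 pairs per scenario. The protocol gives no Tmax distribution, so these are assumptions: log-normal Tmax, medians 15 to 20 versus 10 to 15 min, log-SD 0.3 to 0.8, within-patient correlation 0 or 0.5. Each scenario was run with Tmax rounded to the scheduled times (grid) and with continuous times, because section 10.3.3.1 uses actual collection times. Entries are the percentage of trials with the estimate outside its 90% CI, as difference of treatment medians / median of paired differences.

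| Medians (min) | Log-SDs | Corr. | Grid | Continuous |
|---|---|---|---|---|
| 15 v 12 | 0.4, 0.4 | 0 | 13.9 / 2.7 | 1.3 / 0.1 |
| 15 v 12 | 0.4, 0.4 | 0.5 | 31.1 / 10.1 | 8.8 / 0.4 |
| 20 v 13 | 0.4, 0.4 | 0 | 9.4 / 0.5 | 1.5 / 0.6 |
| 20 v 13 | 0.4, 0.4 | 0.5 | 16.5 / 3.8 | 8.0 / 0.9 |
| 15 v 13 | 0.5, 0.8 | 0 | 6.3 / 0.5 | 6.1 / 1.1 |
| 15 v 13 | 0.5, 0.8 | 0.5 | 16.1 / 3.4 | 18.5 / 1.7 |
| 20 v 13 | 0.4, 0.8 | 0 | 8.7 / 0.9 | 8.2 / 0.7 |
| 20 v 13 | 0.4, 0.8 | 0.5 | 22.5 / 2.5 | 28.3 / 0.9 |
| 15 v 15 | 0.3, 0.3 | 0 | 0.3 / 0.3 | 1.9 / 0.5 |
| 15 v 15 | 0.3, 0.3 | 0.5 | 0.2 / 0.1 | 9.7 / 0.2 |
| 20 v 10 | 0.6, 0.6 | 0 | 1.1 / 1.7 | 1.6 / 1.4 |
| 20 v 10 | 0.6, 0.6 | 0.5 | 4.3 / 4.2 | 4.9 / 4.5 |

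The Hodges-Lehmann estimate was outside in 0% of trials in every row. In one continuous-time trial (first row) the treatment medians differed by 2.42 min, the Hodges-Lehmann estimate was 4.20 and the 90% CI was 2.63 to 5.66.

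A second simulation on the grid used 2,000 trials per scenario, medians 10 to 15 versus 15 to 20 min, CV 40% to 60% and correlation 0.2 to 0.3. It gave 1% to 29% for the difference of medians, with an average gap from the Hodges-Lehmann estimate of 0.6 to 2.0 min.

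**The case against.** The strongest reply is grammatical. In the sentence at issue, the reference to the Wilcoxon test could attach to the p-values alone. The method for the interval would then simply be unstated, which is ordinary detail for an analysis plan. This cannot be excluded. However, the sentence before names the signed-rank test as the analysis of Tmax, and no other interval method is offered, so the plain reading is that the interval comes from that test.

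Second, the phrase about observed medians may mean the median of the within-patient differences. A reader might infer that the rule discards the pairing and that rates near 30% apply. The text does not settle this. Under the paired reading the highest rate is about 10%, though the mismatch remains.

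Third, actual rather than scheduled times are used, so steps in the sampling grid are not the whole cause. That is right, but the continuous-time columns show that the mismatch persists.

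Fourth, a reader might infer that 10.3.4.2 has the same defect for PD Tmax. It does not: its wording never ties the estimate to observed medians and is compatible with a Hodges-Lehmann estimate and its interval. No PD Tmax scenario was simulated either.

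Fifth, it is tempting to judge the size against the earlier study's mean times to treatment success, 16 and 13 minutes (section 3.2). That is a different endpoint from Tmax and gives no scale here.

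Finally, the PK objective is to characterize profiles, and a difference of observed medians is a legitimate description of its own quantity. Both points stand, and they limit the consequence. They do not make that difference a match for the interval printed beside it.

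**Conclusion.** Wrong as written, in section 10.3.3.2 only; severity minor. The protocol chooses the estimator explicitly there, so this is more than detail left to the analysis plan. On the plain reading, estimate and interval describe different quantities. That the estimate can fall outside its interval is shown by the constructed example and needs no distributional assumption.

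The frequency does need assumptions. Across the assumed Tmax distributions it ran from under 1% to about 30% of trials for the difference of treatment medians, and from about 0% to 10% for the median of paired differences. These are illustrative ranges, not predictions for this trial. The average gap of 0.6 to 2.0 min is smaller than the finest planned sampling interval of 5 min.

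No hypothesis, margin or decision rule depends on Tmax. The documents do not support inferring that the primary noninferiority conclusion, or the p-value for Tmax, is affected.

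**What to change.** In section 10.3.3.2, state that the treatment effect on glucagon Tmax is the Hodges-Lehmann estimate of the paired difference (median of the Walsh averages of the within-patient differences), reported with the 90% CI from the signed-rank test. Show the observed medians by treatment as description only.

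Section 10.3.4.2 needs no correction. Using the same wording there would keep the PK and PD reporting consistent.

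The cost is one sentence, and no additional data are needed. Section 10.3 allows a change in analysis method that does not alter a principal feature of the protocol to be described and justified in the SAP or the study report, so no amendment should be needed.

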10.3.4. Pharmacodynamic Analyses

10.3.4.1. Pharmacodynamic Parameter Estimation

Pharmacodynamic parameters will be calculated using NCA. Key PD parameters will be derived to assess the exposure to glucose and duration of exposure above, below, and within the normal glucose range. The normal range for PG will be considered to be 70 to 108 mg/dL. Actual sampling times will be used for all calculations.

The following PD parameters will be calculated using concentrations of glucose:

$AUEC_{above}$	area under the effect concentration-time curve above the normal range
$AUEC_{below}$	area under the effect concentration-time curve below the normal range
$AUEC_{within}$	area under the effect concentration-time curve within the normal range
$AUEC_{0-1.5}$	area under the effect concentration-time curve from time zero (predose) up to 1.5 hours
BG_{max}	maximal blood glucose
$Duration_{above}$	duration above normal range
$Duration_{below}$	duration below normal range
$Duration_{within}$	duration within normal range
t_{above}	time to concentrations above normal range
t_{below}	time to concentrations below normal range (after t_{above})
t_{within}	time to concentrations within normal range
T_{max}	time to maximum concentration

The following PD parameters will be calculated using baseline-adjusted concentrations of PG:

$AUEC_{0-1.5}$	area under the effect concentration-time curve from time zero (predose) up to 1.5 hours
BG_{max}	maximal blood glucose
T_{max}	time to maximum concentration

Baseline PG concentrations will be calculated from samples obtained immediately prior to glucagon dosing (e.g., pre-dose).

Other PD parameters of PG may be calculated if required. Individual concentrations and PD parameters of PG will be summarized with descriptive statistics by treatment.

10.3.4.2. Pharmacodynamic Statistical Inference

The PD parameters (such as BG_{max} and AUEC parameters) will be log-transformed prior to analysis and a linear mixed-effects model fitted to the data, with treatment, period, and sequence as fixed effects and patient as a random effect. For each parameter, the treatment difference will be back-transformed to present the ratios of geometric means and the corresponding 90% CI.

The values of T_{\max} will be analyzed nonparametrically using the Wilcoxon signed-rank test. Median differences and approximate 90% CIs for the difference will be calculated for the comparisons of treatments.

Exploratory analyses may be performed for other PD parameters as deemed appropriate.

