10.3. Statistical Analyses

Statistical analysis of this study will be the responsibility of Eli Lilly and Company or its designee.

Any change to the data analysis methods described in the protocol will require an amendment ONLY if it changes a principal feature of the protocol. Any other change to the data analysis methods described in the protocol, and the justification for making the change, will be described in the statistical analysis plan (SAP) and/or in the clinical study report.

All data will be entered, verified, and archived at a contract research organization (CRO) external to Lilly and/or at Lilly. Data listings, summaries, and analyses will be performed by a CRO and/or by Lilly under the guidance and approval of statisticians at Lilly.

Unless otherwise specified, efficacy analyses will be conducted on all randomized patients who received at least 1 dose of the study drug and have evaluable efficacy outcome.

Pharmacokinetic/pharmacodynamic analyses will be conducted on data from all randomized patients who receive at least 1 dose of the study drug and have evaluable PK/PD.

Safety analyses will be conducted for all randomized patients who receive at least 1 dose of the study drug, whether or not they completed all protocol requirements (see Section 10.3.2.1).

All analyses will be based on the treatment patients actually received (if different from assigned treatment). Unless otherwise specified, all tests of statistical significance for treatment comparisons will be evaluated at a nominal level of 0.05 using 2-tailed test procedures, and confidence intervals (CIs) will be computed as 2-tailed using a 95% significance level. All tests of interactions between treatment group and other covariates will be conducted as 2-sided with an alpha level of 0.10. SAS version 9.2 or higher will be used to perform the analyses.

Additional exploratory analyses of the data will be conducted as deemed appropriate. Study results may be pooled with the results of other studies for population PK analyses purposes to avoid issues with post hoc analyses and incomplete disclosures of analyses.

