10.3.1. Efficacy Analyses

10.3.1.1. Primary Efficacy

The primary outcome is the treatment success, which is defined as an increase in PG to ≥ 70 mg/dL or an increase of ≥ 20 mg/dL from PG nadir within 30 minutes after receiving glucagon, without receiving additional actions to increase the PG concentration. The nadir is defined as the minimum PG concentration at the time of or within 10 minutes following glucagon administration.

The primary analysis will be a treatment group comparison of the primary outcome. The percentage of treatment successes in each treatment and the difference in percentages will be computed. A 2-sided 95% CI will be obtained from the 1-sample mean of the paired differences in primary outcome (1=outcome observed; 0=outcome not observed) across 2 treatment visits. Noninferiority of NG will be declared if the upper limit of a 2-sided 95% CI constructed on the difference in percentages (IMG – NG) is less than the noninferiority margin of 10%.

The proposed noninferiority margin of 10% has been chosen based on the previously completed Phase 3 study (Rickels et al. 2016).

Primary efficacy analysis will only include patients who complete both treatment visits with evaluable primary outcome. The following will be considered as nonevaluable primary efficacy outcome and excluded from the analysis related to primary efficacy outcome:

- Patients with at least 1 treatment visit in which the lowest PG concentration at the time of or within 10 minutes following glucagon administration is ≥ 70 mg/dL;
- Patients receive an external measure to raise PG concentration either before glucagon administration or within the first 10 minutes of glucagon administration.

Plasma glucose concentrations assessed through a central laboratory will be used to assess treatment success. If a central laboratory measurement is missing, the SuperGL (or equivalent)

measurement from that time point will be used in general with the following additional provisions:

- Out-of-window blood draws (blood draws taken before/after the midpoint between consecutive planned measurements) that occur prior to the 30-minute time point will be included.
- Central laboratory PG concentrations and SuperGL (or equivalent) concentrations at the 30-minute time point that are measured more than 35 minutes after administration of glucagon will be considered missing.

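### Section 10.3.4.2 puts AUEC parameters on a log scale, but AUECabove (and less plausibly some other PD parameters) can be exactly zero or non-positive, where the log does not exist

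*Protocol*

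**What the plan says.** Protocol Section 10.3.4.1 sets the reference range: "The normal range for PG will be considered to be 70 to 108 mg/dL". Against that range it defines AUECabove ("area under the effect concentration-time curve above the normal range"), AUECwithin ("area under the effect concentration-time curve within the normal range") and the matching area below. It also lists AUEC0-1.5 and BGmax twice, first on measured glucose and again under the line "The following PD parameters will be calculated using baseline-adjusted concentrations of PG". The baseline is the pre-dose sample. How the adjustment is made is not stated.

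Section 10.3.4.2 then fixes the inference. Naming BGmax and the AUECs as examples, it says the parameters "and AUEC parameters) will be log-transformed prior to analysis and a linear mixed-effects model fitted to the data", with treatment, period and sequence fixed and patient random, and adds: "For each parameter, the treatment difference will be back-transformed to present the ratios of geometric means and the corresponding 90% CI". Only Tmax is given a different method (Wilcoxon signed-rank). Nothing is said about values that are zero or negative, and, unlike Sections 10.3.1.1 to 10.3.2.3, this section does not refer the reader to the SAP.

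On the analysis set, Section 10.3 says PK/PD "analyses will be conducted on data from all randomized patients who receive at least 1 dose of the study drug and have evaluable PK/PD".

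**The concern.** A logarithm exists only for positive numbers. Areas cut at 70 and 108 mg/dL are zero when the curve never enters the region, and a baseline-subtracted area is negative when the early fall outweighs the later rise. For such patient-periods the prescribed analysis has no input value. Mixed-model software then leaves them out unless a rule says otherwise, and the reported ratio applies to a subset defined by the outcome.

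What is at stake is the reading of these supporting PD ratios. A ratio of AUECabove with the zeros omitted compares the two products only over periods in which glucose went above 108 mg/dL. If the gap is noticed only at analysis, the handling of zeros would be chosen with open-label data in view.

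**Working it through.** The plan gives no figure to reproduce here. The check asks whether zeros and non-positive values can occur under the protocol's own rules, and then whether their effect can be sized.

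**Inputs.** Sampling at 0, 5, 10, 15, 20, 25, 30, 40, 50, 60 and 90 minutes (Section 2). Limits 70 and 108 mg/dL (Section 10.3.4.1). Success is glucose of at least 70, or a rise of at least 20 from nadir, within 30 minutes (Section 10.3.1.1). IV-glucose thresholds are below 55 at 30 minutes or below 60 at 45 minutes (Section 9.2.3). Glucose values below are constructed, and areas use the linear trapezoid in mg·h/dL. Subtraction is assumed for baseline adjustment, so adjusted AUEC0-1.5 = raw AUEC0-1.5 − 1.5 × pre-dose value.

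**Profile 1:** 55, 47, 42, 46, 55, 64, 73, 85, 95, 102, 105.
- Success: 73 at 30 minutes.
- Peak 105 is not above 108, so AUECabove = 0.
- Trapezoid segments (mg·min/dL): 255 + 222.5 + 220 + 252.5 + 297.5 + 342.5 + 790 + 900 + 985 + 3105 = 7370; 7370/60 = 122.8.
- AUECwithin = 26.4 and AUECbelow = 8.5. Check: 26.4 − 8.5 = 17.9, against 122.8 − 70 × 1.5 = 17.8 (rounding).
- Adjusted AUEC0-1.5 = 122.8 − 82.5 = +40.3.

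**Profile 2:** 57, 48, 40, 42, 47, 53, 60, 60, 60, 60, 60.
- Success: 60 − 40 = 20. It is not below either IV-glucose threshold.
- Glucose never reaches 70, so AUECabove = 0 and AUECwithin = 0.
- Segments: 262.5 + 220 + 205 + 222.5 + 250 + 282.5 + 600 + 600 + 600 + 1800 = 5042.5; 5042.5/60 = 84.04.
- AUECbelow = 105 − 84.04 = 21.0.
- Adjusted AUEC0-1.5 = 84.04 − 85.5 = −1.46.

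**AUECbelow = 0** needs every value at 70 or more. Section 10.3.1.1 foresees visits where "the lowest PG concentration at the time of or within 10 minutes following glucagon administration is ≥ 70 mg/dL" and removes those patients from the primary efficacy analysis. The PK/PD set in Section 10.3 does not repeat that exclusion.

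**Adjusted BGmax = 0** occurs under subtraction if glucose never rises above the pre-dose value, counting time zero.

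**Illustration of frequency for AUECabove.** Assumed, not in the documents: 66 patients (132 patient-periods); BGmax normal with mean 130–170 (nasal glucagon, NG) and 160–175 mg/dL (intramuscular glucagon, IMG), SD 25–30, within-patient correlation 0.5; a linear rise from 50 at 10 minutes to the 90-minute value.
- Share of zeros = Φ((108 − mean)/SD).
- Across the range, zeros occur in about 1–23% of NG periods and 0.4–4% of IMG periods, so about 1 to 18 of 132 periods are lost.
- Middle case (140 v 160, SD 30): Φ(−1.07) = 0.143 and Φ(−1.73) = 0.042; 66 × (0.143 + 0.042) ≈ 12 periods lost.

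**Direction.** In that middle case the NG/IMG arithmetic ratio on all data is 0.58. The geometric mean ratio on non-zero values is 0.51, and the arithmetic ratio on non-zero values is 0.64. The shift is down or up depending on the scale.

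A second simulation (also assumed: 66 pairs, no true difference, log SD 0.3 between and 0.3 within patients) forced 1, 2 or 5 NG values to zero. When these were the lowest NG values, the log-model ratio rose by 1.2%, 2.2% and 5.0%. When they were placed at random, it did not move (1.000 to 1.001). Sampling error there is SE = 0.3 × √(2/66) = 0.052, giving a 90% CI of about 0.92 to 1.09 around 1, wider than any of these shifts.

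**The case against.** Four arguments limit the point.

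- **Wording.** The text says such as, so it does not claim that every AUEC is logged, and it states no deletion rule. This stands. Omission is what taking the log does by default; the protocol does not prescribe it.
- **SAP territory.** A rule for zeros in supporting parameters is often left to the SAP, and Section 10.3 allows non-principal changes there. This stands in part. An SAP could add the rule, but Section 10.3.4.2 itself fixes the scale, the model and the ratio, and names AUEC parameters as a class. The difficulty lies in what the protocol states, not in what it leaves out.
- **Rarity.** Most routes are remote. The infusion stops below 60 mg/dL and a further fall of 15 to 20 is expected (Section 5.1), so AUECbelow = 0 should be rare. The one NG failure in the predecessor study had reached 70 by 40 minutes (Section 3.2), so AUECwithin = 0 should be uncommon. Profile 2 sits on the boundary of several rules. This stands for all but AUECabove, which needs only a peak of 108 or less.
- **Bias.** A reader might infer that the omitted records are treatment failures, so that the ratio becomes conditional on having responded, or that omission pushes the ratio towards NG. The documents support neither. Profile 1 is a success with AUECabove = 0, so exceeding 108 is not the same as responding. The upward shift appeared only when zeros were imposed on the lowest values of a lognormal distribution that would not itself produce zeros.

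**Conclusion.** The point holds as a minor specification error. The prescribed log analysis cannot be computed for outcomes the protocol allows. This is realistic for AUECabove and less plausible for AUECwithin, AUECbelow and, if adjustment is by subtraction, adjusted AUEC0-1.5 and adjusted BGmax. For AUECabove, the default result is a ratio restricted to periods in which glucose exceeded 108 mg/dL.

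The frequency of such values, and the size and direction of their effect, cannot be determined from the documents; the figures above rest on assumed distributions. The primary analysis, raw BGmax, raw AUEC0-1.5 and Tmax are untouched, and the PD endpoints named in Section 4 are BGmax and Tmax.

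**What to change.** In Section 10.3.4.2:

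- Limit the log model and geometric mean ratios to the strictly positive parameters, raw BGmax and raw AUEC0-1.5.
- Analyse AUECabove, AUECwithin and the baseline-adjusted AUEC0-1.5 and BGmax untransformed in the same mixed model (treatment, period, sequence, random patient). Report the least-squares mean difference with its 90% CI. Include AUECbelow if zeros remain possible in the PD set, as they do under the current definition.
- Report the number of zero or non-positive values per treatment for each of these parameters.
- Give the signed-rank analysis already used for Tmax as a pre-stated sensitivity analysis, always reported.
- State in Section 10.3.4.1 how baseline adjustment is done.

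The cost is a few sentences and no new data. These parameters would be reported as differences instead of ratios, and the untransformed model may fit skewed data with a spike at zero less well. The signed-rank analysis uses complete pairs only and does not adjust for period.
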